### 12.3.2 Serious Adverse Event – Reported within 10 Days

Serious Adverse Events requiring reporting within 10 days (as described in the protocol) must also be reported to the DSMC Chair via an email to [[contact]](mailto:[contact]). The OnCore SAE Details Report must be submitted along with other report materials as appropriate (NCI AdEERS form or FDA Medwatch Form #3500 and/or any other documentation available at the time of initial reporting). The DSMC Chair will review the information and determine if further action is required. All information is entered and tracked in the UWCCC database.

The Principal Investigator notifies all investigators involved with the study at the UWCCC, the IRB, the sponsor, and the funding agency and provides documentation of these notifications to the DSMC.

If the SAE occurs on a clinical trial in which the UW PI serves as the sponsor investigator, the PI reviews the event to determine whether the SAE requires reporting to the FDA and other participating investigators.

For a multiple-institutional clinical trial the PI is responsible for ensuring SAEs are reported to the FDA as well as to all participating investigators.

### 12.3.3 Sponsor-Investigator Responsibilities for SAE Review

In the event the UWCCC Principal Investigator is acting as the Sponsor-Investigator (i.e., the PI holds the IND), the PI assumes responsibilities of the study sponsor in accordance with FDA 21 CFR 312.32. In this capacity, the UWCCC PI reviews all reports of serious adverse events occurring on the study at the UWCCC and participating external sites and makes a determination of 1) **suspectedness** (i.e., whether there is a reasonable possibility that the drug caused the AE); and 2) **unexpectedness** (the event is not listed in the Investigator's Brochure or is not listed at the specificity or severity that has been observed) in the context of this study. SAE with suspected causality to study drug and deemed unexpected are reported as IND Safety Reports by the UWCCC PI to the FDA, all participating investigators on the study, and the external global sponsor (if applicable) within 15 calendar days. All fatal or life-threatening SAE that are unexpected and have suspected causality to the study drug will be reported by the UWCCC PI to the FDA, all participating investigators on the study, and the external global sponsor (if applicable) within 7 calendar days.

Refer to Section 12.5 for UWCCC PI instructions for reporting to the FDA.

### 12.3.4 Study Progress Review

Protocol Summary Reports (PSR) are required to be submitted to the DSMC in the timeframe determined by the risk level of the study (quarterly; semi-annually; or annually). The PSR provides a cumulative report of SAEs, as well as instances of noncompliance, protocol deviations, and unanticipated problems, toxicities and

responses that have occurred on the protocol in the timeframe specified. PSRs for those protocols scheduled for review are reviewed at each DSMC meeting.

Protocol Summary Reports enable DSMC committee members to assess whether significant benefits or risks are occurring that would warrant study suspension or closure. This information is evaluated by the DSMC in conjunction with other reports of quality assurance activities (e.g., reports from Internal Audits, Quality Assurance Reviews) occurring since the prior review of the protocol by the DSMC. Additionally, the DSMC requires the study team to submit external DSMB or DSMC reports, external monitoring findings for industry-sponsored studies, and any other pertinent study-related information

In the event that there is significant risk warranting study suspension or closure, the DSMC will notify the PI of the DSMC findings and ensure the appropriate action is taken for the protocol (e.g., suspension or closure). The DSMC ensures that the PI reports any temporary or permanent suspension of a clinical trial to the sponsor (e.g., NCI Program Director, Industry Sponsor Medical Monitor, Cooperative Group Study Chair) and other appropriate agencies. DSMC findings and requirements for follow-up action are submitted to the CRC.

#### **12.4 Expedited Reporting of Serious Adverse Events**

Depending on the nature, severity, and attribution of the serious adverse event an SAE report will be phoned in, submitted in writing, or both according to Table 5 below. All serious adverse events must also be reported to the UWCCC Data and Safety Monitoring Committee (DSMC) Chair. Serious adverse events must also be reported to the UW IRB per their guidance (<https://kb.wisc.edu/hsirbs/18324#UP>), and any sponsor/funding agency not already included in the list.

Determine the reporting time line for the SAE in question by using the following table. Then refer to sections A and B below if the SAE occurred at the UWCCC or sections C and D if the SAE occurred at a WON Site.

**Table 5. Phase 1 and Early Phase 2 Studies: Expedited Reporting Requirements for Adverse Events that Occur on Studies under an IND/IDE within 30 Days of the Last Administration of the Investigational Agent/Intervention **

**FDA Reporting Requirements for Serious Adverse Events (21 CFR Part 312)**

**NOTE:** Investigators **MUST** immediately report to the University of Wisconsin Carbone Cancer Center and any other parties outlined in the protocol ANY Serious Adverse Events, whether or not they are considered related to the investigational agent(s)/intervention (21 CFR 312.64).

An adverse event is considered serious if it results in ANY of the following outcomes:

- 1) Death.

- 2) A life-threatening adverse event (the patient was at risk of death at the time of the event; it does not refer to an event that hypothetically might have caused death if it were more severe).
- 3) An adverse event that results in inpatient hospitalization or prolongation of existing hospitalization for  $\geq 24$  hours.
- 4) A persistent or significant incapacity or substantial disruption of the ability to conduct normal life functions.
- 5) A congenital anomaly/birth defect.
- 6) Important Medical Events (IME) that may not result in death, be life threatening, or require hospitalization may be considered serious when, based upon medical judgment, they may jeopardize the patient or subject and may require medical or surgical intervention to prevent one of the outcomes listed in this definition (FDA, 21 CFR 312.32; ICH E2A and ICH E6).

**ALL SERIOUS** adverse events that meet the above criteria **MUST** be immediately reported to the UWCCC within the timeframes detailed in the table below:

Hospitalization	Grade 1 and Grade 2 Timeframes	Grade 3-5 Timeframes
Resulting in hospitalization <math>\geq 24</math> hrs	10 Calendar Days	24 Hour; 5 Calendar Days
Not resulting in Hospitalization <math>\geq 24</math> hrs	Not required	

**Expedited AE reporting timelines are defined as:**

- **24-Hour; 5 Calendar Days** – The AE must initially be reported within 24 hours of learning of the AE, followed by a complete expedited report within 5 calendar days of the initial 24-hour report.
- **10 Calendar Days** – A complete expedited report on the AE must be submitted within 10 calendar days of learning of the AE

 Serious adverse events that occur more than 30 days after the last administration of investigational agent/intervention and have an attribution of possible, probable, or definite require reporting as follows:

**Expedited 24-hour notification followed by complete report within 5 calendar days for:**

- All Grade 3, 4, and 5 AEs

**Expedited 10 calendar day reports for:**

- Grade 2 AEs resulting in hospitalization or prolongation of hospitalization

 For studies using PET or SPECT IND agents, the AE reporting period is limited to 10 radioactive half-lives, rounded UP to the nearest whole day, after the agent/intervention was last administered. Footnote "1" above applies after this reporting period.

#### 12.4.1 SAE Requiring 24 hour Reporting Occurs at UWCCC:

##### 12.4.1.1 Report to the UWCCC:

Reference the **SAE SOP** (Standard Operating Procedure) and the **SAE Reporting Workflow for DOTs** on the UWCCC website (<https://kb.wisc.edu/uwccc/internal/page.php?id=54655>) for specific instructions on how and what to report to the UWCCC for [24] hour initial and follow-up reports. **A follow-up report is required to be submitted within 5 calendar days of the initial [24] hour report.**

For this protocol, the following UWCCC entities are required to be notified:

- a. UWCCC DSMC: [[contact]](mailto:[contact])
- b. UWCCC PI: [name]
- c. UWCCC Breast Clinical Team Manager: [name]
- d. Any other appropriate parties listed on the SAE Routing Form

##### 12.4.1.2 Report to the Sponsor:

Serious adverse events (whether or not related to study drugs) will also be reported to Oncoceutics or designee within 24 hours from the time the Investigator first becomes aware of the SAE. After the initial SAE notification to Oncoceutics or designee, follow-up SAE information will be submitted each time that important follow-up information (e.g., diagnosis, outcome, causality assessment, results of specific investigations) becomes available.

Any serious adverse event, or follow up to a serious adverse event, including death due to any cause other than progression of the cancer under study that occurs to any subject from the time of initiation of therapy through 30 days following cessation of treatment, or the initiation of new anti-cancer therapy, whichever is earlier, must be reported to Oncoceutics. This applies whether or not the event is related to ONC201.

If serious medical occurrences, including death, occur outside of the safety follow-up window established by the protocol and are reported to or observed by the Investigator to be related to the administration of the investigational product, it is the Investigator's responsibility to report this occurrence to Oncoceutics or designee within 24 hours from the time site personnel become aware of the occurrence.

In addition to SAEs, the following reportable events must also be submitted to Oncoceutics within 24 hours from the time the Investigator first becomes aware of them:

- Exposure during Pregnancy or Breastfeeding (even if not associated with an adverse event)

- Occupational exposure (even if not associated with an adverse event)  
Reports should be made to Oncoceutics using FDA form 3500A (MedWatch) or the UWCCC SAE form may be used.

**Specifying:**

- PROTOCOL Number
- SUBJECT Number
- SITE Number/PI Name
- SAE/ONSET DATE

**12.4.1.3 Report to the IRB:**

Consult the UW Health Sciences website (<https://kb.wisc.edu/hsirbs/18324#UP>) for reporting guidelines.

**12.4.2 SAE Requiring 10 Day Reporting Occurs at UWCCC:**

**12.4.2.1 Report to the UWCCC:**

Reference the **SAE SOP** and the **SAE Reporting Workflow for DOTs** on the UWCCC website (<https://kb.wisc.edu/uwccc/internal/page.php?id=54655>) for specific instructions on how and what to report to the UWCCC for [10] day reports.

For this protocol, the following entities are required to be notified:

- a. UWCCC DSMC: [[contact]](mailto:[contact])
- b. Any appropriate parties listed on SAE Routing form

**12.4.2.2 Report to the Sponsor:**

See section 12.4.1.2 - SAEs must be reported to Oncoceutics or designee within 24 hours.

**12.4.2.3 Report to the IRB:**

Consult the UW Health Sciences IRB website (<https://kb.wisc.edu/hsirbs/18324#UP>) for reporting guidelines.

**12.4.3 SAE Requiring 24 Hour Reporting Occurs at a WON Site:**

**12.4.3.1 Report to the UWCCC:**

Reference the **SAE SOP** and the **SAE Reporting Workflow for 1SP, JC, and other Affiliates** on the UWCCC website (<https://kb.wisc.edu/uwccc/internal/page.php?id=54655>) for specific instructions on how and what to report to the UWCCC for [24] hour initial and follow-up

reports. A follow-up report is required to be submitted within 5 calendar days of the initial [24] hour report.

Send the OnCore SAE details report and any supporting, applicable documentation to: [[contact]](mailto:[contact])

**NOTE:** After a WON site has submitted the [24] hour SAE follow-up report, the report is triaged initially to the UW Principal Investigator or Study Chair, the DOT Program Manager, the Affiliate Coordinator, and the DSMC Chair for review. **The Principal Investigator is then responsible for ensuring the SAE is reported to the FDA, the global sponsor (if applicable), the UW IRB, and any other entity requiring notification, in accordance each entities' reporting requirements.**

**12.4.3.2 Report to the Sponsor:**

The UW Principal Investigator is responsible for ensuring the SAE is reported to the sponsor, Oncoceutics.

**12.4.3.3 Report to the IRB:**

WON sites should follow their own local IRB reporting guidelines for SAE submission. The UW PI is responsible for the submission of the SAE to the UW Health Sciences IRBs for any site for which the UW serves as the IRB of record. Additionally, the UW PI is responsible for the submission of the SAE to the UW Health Sciences IRB for any site if it meets the definition of unanticipated problem.

**12.4.4 SAE Requiring 10 Day Reporting Occurs at a WON site:**

**12.4.4.1 Report to the UWCCC:**

Reference the **SAE SOP** and the **SAE Reporting Workflow for 1SP, JC, and other Affiliates** on the UWCCC website (<https://kb.wisc.edu/uwccc/internal/page.php?id=54655>) for specific instructions on how and what to report to the UWCCC for [10] day reports.

Send the OnCore SAE details report and any supporting, applicable documentation to: [[contact]](mailto:[contact])

**NOTE:** After a WON site has submitted the [10] day SAE follow-up report, the report is triaged initially to the UW Principal Investigator or Study Chair, the DOT Program Manager, the Affiliate Coordinator, and the DSMC Chair for review. **The Principal Investigator is then responsible for ensuring the SAE is reported to the FDA, the global sponsor (if applicable), the UW IRB, and any other entity requiring notification, in accordance each entities' reporting requirements.**

**12.4.4.2 Report to the Sponsor:**

The UW Principal Investigator is responsible for ensuring the SAE is reported to the sponsor, Oncoceutics.

#### 12.4.4.3 Report to the IRB:

WON sites should follow their local IRB reporting guidelines for SAE submission. The UW PI is responsible for the submission of the SAE to the UW Health Sciences IRBs for any site for which the UW serves as the IRB of record. Additionally, the UW PI is responsible for the submission of the SAE to the UW Health Sciences IRB for any site if it meets the definition of an unanticipated problem.

### 12.5 Other Reporting Requirements

#### Reporting to the FDA

Serious Adverse Events occurring on studies on which a UW PI is acting as sponsor-investigator must be reported to the FDA as determined by the completion of the UW Sponsor-Investigator Determination Form for FDA Reporting of Safety Events. Mandatory and voluntary reporting guidelines and instructions are outlined on the FDA website: <http://www.fda.gov/Safety/MedWatch/HowToReport/default.htm>

## 13. STATISTICAL METHODS

### 13.1 Study design

We propose a phase II clinical trial, non-randomized, single arm, open label study of the combination of ONC201 with ONC201 with intermittent MR diet in patients with metastatic TNBC.

Accrual is competitive such that each site can contribute any number of subjects until the study maximum of 34 is reached.

The primary objective is to evaluate the rate of patients with objective response to ONC201 with a MR diet.

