	
WBRT >28 days ago will be eligible if asymptomatic and off systemic steroids.
 

6. Life expectancy of greater than 12 weeks.

7. Normal organ and marrow function as defined per protocol definitions.

8. Excludes patients who follow a vegan or vegetarian diet

STATISTICAL CONSIDERATIONS	
The primary objective is to evaluate efficacy of ONC201 with a methionine-restricted diet in metastatic TNBC. The study is designed as a single-arm phase II trial. The primary endpoint is ORR. Secondary endpoints include CBR, PFS, OS, safety, metabolic indices and CTC TRAIL-receptor expression. The null hypothesis is that the probability of ORR is no more than 0.1, i.e., <math>H_0: p \leq 0.1</math>, and the alternative hypothesis is <math>H_1: p \geq 0.25</math>. In this single arm study, a Simon's two stage design will be utilized. The null hypothesis that the true ORR is 0.1 will be tested against a one-sided alternative. The study will be powered to detect an ORR of 25% with the combination of ONC201 with a methionine-restricted diet, using a power of 80% and a type I error rate of 10%. The first stage sample size will be 13. After testing the combination on 13 subjects in the first stage, the trial will be terminated if 1 or fewer subjects respond. If the trial goes on to the second stage, a total of 34 subjects will be studied (i.e. additional 21 subjects will be recruited). If the total number responding or having ORR is less than or equal to 5, the combination of ONC201 with a methionine-restricted diet will be rejected.
 
Time to event outcomes such as PFS and OS will be analyzed using Kaplan-Meier method and Cox proportional hazards regression.

TOTAL NUMBER OF SUBJECTS	Number of subjects in the phase II study: 34
ESTIMATED ENROLLMENT PERIOD	Estimated 30 months
ESTIMATED STUDY DURATION	Estimated 36 months

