### 13.2 Sample size and accrual

The primary objective is to evaluate efficacy of ONC-201 with dietary MR in metastatic TNBC. The study is designed as a single-arm phase II trial. The primary endpoint is ORR. Secondary endpoints include CBR at 4 months, PFS, OS, safety, metabolic indices and CTC TRAIL-receptor expression. The null hypothesis is that the probability of overall response is no more than 0.1, *i.e.*,  $H_0: p \leq 0.1$ , and the alternative hypothesis is  $H_1: p \geq 0.25$ .

In this single arm study, a Simon's two stage design will be utilized. The null hypothesis that the true ORR is 0.1 will be tested against a one-sided alternative. The study will be powered to detect an ORR of 25% with the combination of ONC201 with a methionine-restricted diet, using a power of 80% and a type I error rate of 10%. The first stage sample size will be 13. After testing the combination on 13 subjects in the first stage, the trial will be terminated if 1 or fewer subjects respond. If the trial goes on to the second stage, a total of 34 subjects will be studied (*i.e.* additional 21 subjects will be recruited). If the total number responding or having ORR is less than or equal to 5, the combination of ONC201 with a methionine-restricted diet will be rejected.

The estimated total sample size for the study is 34 subjects.

One subject was enrolled to the ONC201 +MR diet prior to changing the dosing schedule. This subject will be replaced for efficacy analysis, but will be considered part of the safety analysis.

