### **13.3 Analysis datasets**

Population	Definition
Evaluable for Safety	This will comprise all subjects who receive at least one dose of trial drug and either undergo at least one post-baseline assessment or die before any evaluation.
Evaluable for Efficacy	This will comprise all subjects who receive at least 80% of ONC201 + MR diet doses during the first two cycles of treatment (i.e., at least 9 doses of ONC201) and have at least one disease re-evaluation. Subjects who are not evaluable for response, however, will be replaced.

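### The accrual maximum of 34 does not fit the replacement rules: with 34 needed for efficacy and one enrolled subject already counted for safety only, at least 35 must be enrolled.

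*Combined protocol and SAP*

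**What the plan says.** Section 13.1 tells sites when accrual stops: "Accrual is competitive such that each site can contribute any number of subjects until the study maximum of 34 is reached". The synopsis entry for the total reads "Number of subjects in the phase II study: 34". Section 13.2 also gives 34 as the estimated total sample size.

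Section 13.2 sets out the Simon two-stage design. "The first stage sample size will be 13", and the trial stops if at most 1 of those subjects responds. Otherwise 21 more are recruited, and the combination is rejected if at most 5 of the 34 respond. The null response rate is 10%, the alternative 25%, the power 80% and the one-sided type I error 10%.

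Three provisions remove subjects from the efficacy count and call for others in their place:

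- Section 13.2, on a subject enrolled before the dosing schedule changed: "This subject will be replaced for efficacy analysis, but will be considered part of the safety analysis".
- Section 13.3, on the efficacy set: "Subjects who are not evaluable for response, however, will be replaced".
- Section 4.2 allows replacement of a registered subject who never starts protocol therapy or the diet.

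The documents do not say whether 34 counts enrolled or evaluable subjects. They give no larger enrolment ceiling and no expected non-evaluable rate.

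**The concern.** The decision rule of 5 out of 34 has its stated properties only if 34 subjects enter the efficacy analysis. The subject treated under the old schedule has been enrolled and stays in the safety analysis, but does not count towards that 34. Thirty-four efficacy subjects plus this one make 35, which is above the stated maximum and total. Each further non-evaluable subject who is replaced adds one more.

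This matters because the sentence in Section 13.1 is the operational stopping instruction for several sites accruing in competition. If they stop at 34 enrolled, the replacements cannot be made, and an unchanged cut-off of 5 is applied to a smaller group, which costs power. If they continue so that replacements can be made, the study exceeds its own stated maximum. Either way a stated number has to change, and the plan should say which.

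**Working it through.** **Inputs.** From Section 13.2: p0 = 0.10, p1 = 0.25, n1 = 13, r1 = 1, n = 34, r = 5, and one enrolled subject excluded from efficacy. From Section 13.1 and the synopsis: 34 as maximum and total.

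**Formula.** With X1 responders among the first 13 and X2 among the remaining n − 13,

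P(declare active | p) = Σ over x = 2,…,13 of P(X1 = x) × P(X2 ≥ 6 − x), where X1 ~ Bin(13, p) and X2 ~ Bin(n − 13, p).

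**Step 1: reproduce the plan's design (n = 34).**

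- Early stopping under p0: 0.9^13 + 13 × 0.1 × 0.9^12 = 0.621.
- Early stopping under p1: 0.75^13 + 13 × 0.25 × 0.75^12 = 0.127.
- Type I error: 0.0957. Power: 0.8108.

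Both stated targets (10% and 80%) are met. A search over two-stage designs shows that this is the optimal Simon design for these rates: it has the smallest expected sample size under p0, 13 + 21 × (1 − 0.621) = 20.95. The sample-size calculation is sound.

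**Step 2: count the subjects.** Needed for efficacy: 13 + 21 = 34. Enrolled but counted for safety only: 1. Minimum enrolment: 34 + 1 = 35. If enrolment is held at 34, at most 34 − 1 = 33 can be in the efficacy analysis.

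**Step 3: apply the same cut-offs (1 of 13, then 5) to a smaller total.**

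| Evaluable n | Further unreplaced losses beyond the known one | Type I error | Power at 25% |
|---|---|---|---|
| 34 | (known subject replaced) | 9.57% | 81.1% |
| 33 | 0 | 8.74% | 79.85% |
| 32 | 1 | 7.93% | 78.4% |
| 31 | 2 | 7.14% | 76.7% |
| 30 | 3 | 6.39% | 74.8% |
| 28 | 5 | 4.98% | 70.0% |

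Only the row for 33 rests on a documented loss, and it costs 81.1 − 79.85 ≈ 1.2 points. The rows below it are illustrations, because the documents give no number of further losses. Type I error falls throughout, so there is no added false-positive risk.

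**Step 4: enrolment that would deliver 34 evaluable.** For an assumed non-evaluable rate d, round 34/(1 − d) up and add 1 for the known subject:

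- d = 0: 34 + 1 = 35
- d = 5%: 35.8 → 36, + 1 = 37
- d = 10%: 37.8 → 38, + 1 = 39
- d = 15%: 40 + 1 = 41
- d = 20%: 42.5 → 43, + 1 = 44

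The rates are assumptions. The ceilings cover the expected number of losses and do not guarantee 34 evaluable.

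**The case against.** The best defence is that the plan already provides the remedy. In ordinary use a replaced subject does not count towards the target. On that reading 34 is the efficacy number, replacements are accrued on top, and the full 81.1% power is available. The synopsis entry does not mention a maximum or enrolment, and Section 13.2 calls its total an estimate. Only Section 13.1 speaks of a maximum, in a sentence whose purpose is to explain competitive accrual.

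Much of this stands. A reader might infer from the cap that 34 evaluable subjects and 80% power cannot be reached. The documents do not support that. The replacement clauses can be read as keeping 34 evaluable within reach. Even under a literal cap, the one documented loss leaves 79.85%, which rounds to the stated 80%. A material loss needs further subjects who are non-evaluable and not replaced, and Section 13.3 says such subjects are replaced.

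The defence does not rescue the text as written. If replaced subjects fall outside the 34, the study enrols at least 35, and the maximum in Section 13.1 and the synopsis total are too low. More non-evaluable subjects are also plausible under the plan's own rules. Efficacy evaluability requires a minimum number of doses over two cycles and a disease re-evaluation (Sections 6.4 and 13.3). The first scheduled re-scan comes at about 9 weeks (Section 7, note 10). Eligibility allows any number of prior lines and asks only for life expectancy above 12 weeks (Sections 3.1.5 and 3.1.9).

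**Conclusion.** The maximum and total of 34 conflict with the replacement rules, and the conflict needs correcting. It is a fault in how the sample size is stated; the Simon calculation is right. The certain part is small: enrolment must be at least 35, or else the final rule is applied to at most 33 subjects with power 79.85% instead of 81.1%, and with type I error 8.7% instead of 9.6%. Anything larger is conditional on an unstated number of unreplaced losses, for example 76.7% with 31 evaluable or 70.0% with 28.

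The power figures assume that the cut-offs stay at 1 and 5, that the first stage still has 13 evaluable subjects, and that evaluable subjects respond at 25% whatever the reason others are not evaluable. They also take the evaluable set of Section 13.3 as the denominator. Section 13.7.1 instead divides by subjects with measurable disease and counts missing data as non-response; that mismatch is a separate matter.

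**What to change.** In the synopsis and Sections 13.1 and 13.2, state that 13 and 34 are numbers of subjects evaluable for efficacy. Replace the accrual maximum of 34 with a separate enrolment ceiling: at least 35, plus an allowance for replacements under a stated non-evaluable rate. Ceilings of 37, 39 or 44 correspond to assumed rates of 5%, 10% or 20%. Restate the synopsis total to match.

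If 34 enrolled is a true cap, remove the replacement promises in Sections 4.2, 13.2 and 13.3 and restate the power for the evaluable number expected: 79.85% at 33, lower if more losses are foreseen.

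The cost is wording, plus a stated accrual or power slightly less favourable than now. If the synopsis's 30 months was meant for 34 enrolled at a steady rate, each additional subject adds about 30/34 = 0.88 month. The replacement rules already imply that extra accrual; the change makes it visible.
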